- Cohort 1: Subjects from group 1 and group 2 will be scheduled for three study sessions as described below. A screening visit, an MR spectroscopy scan without hyperinsulinemic clamp (euglycemia) and an MR spectroscopy scan during a hyperinsulinemic clamp (hypoglycemia) with a tracer infusion.
- Cohort 2: Subjects from group 1 and group 2 will be scheduled for two study sessions. A screening visit as described below. An MR spectroscopy scan that will be conducted during a hyperinsulinemic clamp (combined eu- and hypoglycemia) together with a tracer infusion.
- Cohort 3: Subjects from group 1 and group 2 will be scheduled for two studysessions. A screening visit as described below. An MR spectroscopy scan conducted during a hyperinsulinemic clamp (combined eu- and hypoglycemia) without a tracerinfusion.
- Cohort 4: Healthy subjects from group 2 will be scheduled for one study session. They will undergo an MR spectroscopy scan without a hyperinsulinemic clamp nor any other i.v. infusions (i.e. no i.v. infusions at all).
- Cohort 5: Subjects from group 1 and group 2 will be scheduled for two studysessions. A screening visit as described below and a hyperinsulinemic clamp together with a non-labeled ketone or saline infusion without an MR spectroscopy scan.

Session A: Screening visit (YNHH Clinical Research Unit):

At the screening visit, study subjects in both the control and T1DM groups will complete the informed consent form for participation in voluntary clinical research. Demographic and clinical data collected will be reviewed by study personnel to confirm eligibility.

Once consented, all subjects will be further screened with a medical history & physical examination, blood work (electrolytes, hematocrit, creatinine, liver function tests and HbA1c) and a 12-lead electrocardiogram (EKG). Detailed subject inclusion and exclusion criteria are listed below (Human subjects – Subject recruitment). Subjects in the T1DM group only will be instructed to record their glucose readings to determine degree and frequency of hypoglycemia as described above. The subject will perform the preliminary cognitive tests at this point if they are selected for Cohort 5 at this point. The two subsequent MR sessions to complete the study will be scheduled at this point. The subject in the control group will have their two MR sessions scheduled without having to record any glucose readings.

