Session B: NMR spectroscopy without tracer infusion (Magnetic Resonance Research Center)

Subjects may be scheduled to arrive on the evening before the study if arriving early will be a difficulty. If such a case occurs, subjects will be admitted to the HRU for an overnight stay to be there for the morning without any delay.

On the morning of study, subjects will arrive directly at the MRRC. A member of the research team will verify that if the subject is from the T1DM group, the diabetic subject (as previously instructed) has taken his/her normal morning dose of insulin (or has continued to wear the insulin pump). This will not apply to subjects that are from the control group of non-diabetics participants. A urine pregnancy test will be completed on all female subjects of child bearing potential. Any female testing positive will be excluded from the study. All subjects will meet the staff, study procedures will be reviewed, and they will be exposed to the instrumentation and then placed in the scanner for NMR spectroscopy.

Imaging Procedures with the 4T/ 7T Bruker Advance NMR spectrometer (Bruker Instruments, Inc, Bellerica, MA) with a 94 cm bore: Proton MRS will be performed using the outer 1H decoupling coils of the ¹³C probe at 4T. Parameters and pulse sequences for GABA and glutamate acquisition will be the standard ones presently being established for this coil by Drs [name] and [name]: Subjects will lie supine with the occipital cortex against a 7-cm surface coil tuned to ¹H-MRS frequency of 170.4 MHz. T₁-weighted images 30 seconds in duration will be acquired for subject positioning. 1st and 2nd order shimming will be performed automatically using the FASTERMAP procedure. We will then proceed to acquiring proton NMR spectra from a volume adjacent to the NMR coil for a period of 60 minutes. Total and regional power deposition will be below the FDA safety limits for RF power deposition. For 7T studies the pulse sequence will be performed using the multi Tx coil using pulse sequences and parameters established by Dr [name], which will be verified regarding local power deposition using RF simulations. The 7T studies will be exploratory.

Session C: NMR spectroscopy with ¹³C/ ²H -tracer infusion (Magnetic Resonance Research Center)

[figure not shown]

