Non-diabetic control subjects will be asked to remain fasting from midnight prior to the study. Upon arrival to the MRRC, their blood glucose will be checked and an IV catheter will be inserted for infusion of insulin and glucose to maintain normal glucose levels and the study will ensue as described below.

For type 1 diabetic subjects receiving insulin via an insulin pump, they will be asked to check their blood glucose at home before bed and on awakening to ensure that the glucose level is above 70mg/dl and below 200mg/dl. They will be instructed to call [name] with any readings outside of this range. Upon arrival to the MRRC, their blood glucose will be checked as a safeguard, and insulin received via the insulin pump will be held. An IV catheter will be inserted for infusion of insulin and glucose to maintain normal glucose levels and the study will ensue as described below.

For type 1 diabetic subjects using multiple injections of insulin per day will be asked to ensure that the glucose level is above 70mg/dl and below 200mg/dl. As a safeguard, they

will be asked to check their blood glucose at home before bed and on awakening. Upon arrival to MRRC, their blood glucose will be checked; a nurse will place intravenous (IV) line to start infusions of glucose and insulin to maintain normal glucose levels.

At 9:00 AM on the day of this NMR session, a standard IV catheter will be inserted and used to deliver a continuous

MRS study design. After a set up period of approximately 30 minutes that includes a 1H MRS scan, subjects will be infused for 120minutes with the isotopic labeled substrate.

insulin infusion (2mU/kg/min) and a variable infusion of 20% dextrose. In addition a second IV line will be placed in the opposite arm to receive a normal saline solution and provide access for obtaining blood samples.

Once subjects arrive in the MR center they will be brought to a hypoglycemic state. The plasma glucose level will be gently lowered to 50 ± 3 mg/dL (see blood draw schedule below).

Once hypoglycemia is achieved tracer will be administered (see Figure above). Depending on the cohort assignment this will involve one of the following infusions:

 a) A 200mmol/l ¹³C /²H- alternate substrate infusion, which will be delivered through a port in the already-established IV site at a rate of 22μM/kg/min.

or

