Then a cognitive testing battery is administered via questionnaire as done by our group before (HIC#0505000079; PI: [name]). Tests of non-memory function included digit symbol substitution, Tests of Everyday Attention, telephone book searching, and map searching in 1 and 2min. Tests of immediate and delayed verbal memory and verbal memory recognition are adapted from the Wechsler Memory Scale logical memory tests. Working memory will be assessed by modified versions of the standard Wechsler Memory Scale Digit Span and Letter/Number Sequencing Tests, and map searching.

Throughout, blood is obtained for glucose, BHB, lactate, insulin, glucagon, cortisol, and catecholamines and will be assayed using established RIA, HPLC & ELISA methods in the YCCI Core Lab (see blood draw schedule below).

Blood Draw Schedule

	start hypo clamp	glucose ~55mg/dl for ~10-15min	glucose ~55mg/dl for ~20-25min							
Timeline	-60 min	-10 min	¹³ C/ ² H-tracer Baseline start infusion*	+5	+10	+15	+30	+60	+90	+120
Insulin	X		X			Х	Χ	Х		Х
Ketones	X		X			Х	Х	Х		Х
Lactate	X		Х			Х	Х	Х	Х	Х
C ¹³ / ² H enrichment (during tracer infusion study)			Х	X	Х	Х	Х	Х	Х	Х
Counterreg.	Х	Х	Х				Х	Х		Х
glucose	glucose every 5 min during hypo clampglucose every 5 min during hypo clamp									

^{*} blood draws timed to alternate fuel infusion Counter-regulatory hormones = E, NE, glucagon, cortisol, growth hormone

In the event that scheduling issues preclude the sequencing of scanning sessions as described above, certain modifications can be made to accommodate a subject.

Blood Volumes and Schedule of Events Tables for each group are included at the end of this application.

5. Genetic Testing N/A

A. Describe

- i. the types of future research to be conducted using the materials, specifying if immortalization of cell lines, whole exome or genome sequencing, genome wide association studies, or animal studies are planned
- ii. the plan for the collection of material or the conditions under which material will be received
- iii. the types of information about the donor/individual contributors that will be entered into a database
- iv. the methods to uphold confidentiality
- **B.** What are the conditions or procedures for sharing of materials and/or distributing for future research projects?
- **C.** Is widespread sharing of materials planned?
- **D.** When and under what conditions will materials be stripped of all identifiers?

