B.1	Start insulin/ start clock	Glucose is checked every 5 minutes	X	X	X				Enter scanner
B.2	B.1 +30	X	X	X	X				
B.3	B.1 +60	X	X	X	X				
B.4	B.1 +90	X	X	X	X				
C.1 BHB Baseline	Start BHB infusion	Glucose is checked q5 min	X	X	X	X	X	X	Target glucose ~55mg/dl
C.2	C.1 +5	\downarrow				X			
C.3	C.1 +10	1				X			↓
C.4	C.1 +15	1				X			↓
C.5	C.1 +30	1	X	X	X	X	X		↓
C.6	C.1 +60	1	X	X	X	X	X	X	↓
C.7	C.1 +90	1	X	X	X	X	X		 
C.8	C.1 +120	Glucose check	X	X	X	X	X	X	End Clamp

COHORT 1:

Schedule of Events:	Screening Visit Session A	Proton-NMR Spectroscopy Session B	Carbon 13-NMR Spectroscopy Session C	Total Blood Collected
Informed Consent	X			
Medical History	X			
Physical Exam	X			
EKG	X			
Hematocrit (3 mLs)	X (3mLs)			
Creatinine (2 mLs)	X (2mLs)			
Liver Function Tests (3mLs)	X (3mLs)			
HbA1c (3mLs)	X (3mLs)			
Inclusion/Exclusion Check list	X			
Record Blood Sugar Levels 5x daily *	X			
Complete questionnaire for glucose readings <54mg/dl *	X			
Schedule two MR sessions	X			
Urine Pregnancy (females)	X	X		
IV Placement			X	
Hypoglycemic Clamp			X	
Blood Volume per visit	11 ml	none	< 250ml	< 250ml

^{*:} For diabetic subjects only

COHORT 2:

Schedule of Events:	Screening Visit	Carbon 13-NMR Spectroscopy	Total Blood Collected
Informed Consont	Session A	Session C	
Informed Consent	X		
Medical History	X		
Physical Exam	X		
EKG	X		
Hematocrit (3 mLs)	X (3mLs)		
Creatinine (2 mLs)	X (2mLs)		
Liver Function Tests (3mLs)	X (3mLs)		
HbA1c (3mLs)	X (3mLs)		
Inclusion/Exclusion Check list	X		
Record Blood Sugar Levels 5x daily *	X		
Complete questionnaire for glucose readings <54mg/dl *	X		
Schedule MR sessions	X		
Urine Pregnancy (females)	X	X	
IV Placement		X	
Hypoglycemic Clamp		X	
Blood Volume per visit	11 ml	< 250ml	< 250 ml

^{*:} For diabetic subjects only

COHORT 3:

Schedule of Events:	Screening	Proton-NMR	Total Blood
	Visit	Spectroscopy	Collected
	Session A	Session B	
Informed Consent	X		
Medical History	X		
Physical Exam	X		
EKG	X		
Hematocrit (3 mLs)	X (3mLs)		
Creatinine (2 mLs)	X (2mLs)		
Liver Function Tests (3mLs)	X (3mLs)		
HbA1c (3mLs)	X (3mLs)		
Inclusion/Exclusion Check list	X		
Record Blood Sugar Levels 5x daily *	X		
Complete questionnaire for glucose readings <54mg/dl *	X		
Schedule MR sessions	X		
Urine Pregnancy (females)	X	X	
IV Placement		X	
Hypoglycemic Clamp		X	
Blood Volume per visit	11 ml	< 250ml	< 250 ml

^{*:} For diabetic subjects only

COHORT 4:

Schedule of Events:	Screening Visit Session A	Proton-NMR Spectroscopy Session B

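### The Cohort 1 schedule shows no pregnancy test at Session C, the only Cohort 1 visit with insulin, clamped hypoglycemia and tracer

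*Combined protocol and SAP*

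**What the plan says.** Section V, item 4 gives Cohort 1 a screening visit, then "an MR spectroscopy scan without hyperinsulinemic clamp (euglycemia) and an MR spectroscopy scan during a hyperinsulinemic clamp (hypoglycemia) with a tracer infusion". The first scan is Session B and the second is Session C.

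The Session B text contains the only study-day testing rule in the narrative: "A urine pregnancy test will be completed on all female subjects of child bearing potential". It adds the consequence: "Any female testing positive will be excluded from the study".

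The Session C text gives arrival steps for three kinds of participant. For non-diabetic controls, after the overnight fast, it says: "Upon arrival to the MRRC, their blood glucose will be checked and an IV catheter will be inserted for infusion of insulin and glucose". The paragraphs for pump users and for those on multiple injections also go from a glucose check to an IV line. None of the three mentions a pregnancy test.

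In the Cohort 1 Schedule of Events at the end of the protocol, the third visit column is headed "Carbon 13-NMR Spectroscopy Session C". IV placement and the clamp are marked there and nowhere else in that table. The urine pregnancy row is marked for Sessions A and B only. The row "Inclusion/Exclusion Check list" is marked for Session A only.

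A note after the blood draw schedule in Section V, item 4 says that if "scheduling issues preclude the sequencing of scanning sessions as described above, certain modifications can be made to accommodate a subject".

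**The concern.** Pregnancy is the first exclusion in Section V, item 8. A pregnancy test guards against exposing a pregnant woman only if it is recent when the exposure begins. In Cohort 1 that exposure comes at Session C: insulin at 2 mU/kg/min, plasma glucose lowered to about 50 mg/dL, and a tracer infusion. Session B is a scan with no clamp and no tracer. The schedule therefore places the test at the lower-exposure visit and shows none at the higher-exposure one.

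A pregnancy first detectable after the last scheduled test could go unnoticed before the clamp. The study team rates the study as moderate risk (Section V, item 12) and expects no direct medical benefit to participants (Section IX). That leaves little reason to accept an avoidable gap in applying a listed exclusion.

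**Working it through.** There is no power or sample-size figure to reproduce. The check is a cell-by-cell reading of the schedules against the text.

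**Cohort 1 table, selected rows**

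| Row | Session A | Session B | Session C |
|---|---|---|---|
| Urine pregnancy test | marked | marked | blank |
| IV placement | blank | blank | marked |
| Hypoglycemic clamp | blank | blank | marked |
| Blood volume | 11 ml | none | < 250 ml |

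The IV, clamp and blood-volume entries fall where the cohort definition says they should, so the columns have not shifted.

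**Clamp-day columns across cohorts**

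| Cohort | Clamp visit in its table | Pregnancy test marked |
|---|---|---|
| 1 | Session C | no |
| 2 | Session C | yes |
| 3 | Session B | yes |
| 5 | Session D | yes |

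- Clamp-day columns with the test: 3 of 4.
- All visit columns, Cohorts 1 to 5: 3 + 2 + 2 + 2 + 2 = 11.
- Visit columns with the test: 2 + 2 + 2 + 2 + 2 = 10. The single column without it is Cohort 1, Session C.

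Cohort 4 has no infusion at all, yet its table marks the test at both of its columns.

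**Other mentions of pregnancy.** Outside the schedules and the Session B text, pregnancy appears in:

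- the subject classification and exclusion list (Section V, items 7 and 8);
- the recruitment text and screening procedures (Section VII, items 3 and 4);
- the list of health information collected (Section VIII);
- the statement on costs to participants (Section X, item 3).

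Of these, only the screening procedures schedule a test, and that one is at Session A. None requires a test at Cohort 1 Session C.

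**How old the last test could be**

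- *Order A, B, C.* The last test is at Session B. No maximum interval from B to C is given, so its age at the clamp is undefined.
- *Order A, C, B,* if the sequencing note is used that way. The last scheduled test is at screening. Participants with type 1 diabetes are told at screening to record glucose, and the HYPO score needed for enrollment uses a 4-week record. Their test could then be about four weeks old or more. This is inferred from the stated steps; the protocol gives no such interval.

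**The case against.** The strongest reply is that the finding rests on one empty cell in a table read from PDF, and that the next table (Cohort 2) is visibly damaged in its header. Correct alignment of the other rows argues against a column shift but does not exclude one dropped mark. That doubt stands.

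The silence of the Session C text is also weak support by itself. The same text serves Cohort 2, whose table does schedule the test. The Session D text is silent too, while the Cohort 5 table schedules the test. In this protocol a silent narrative does not mean that no test is done. Likewise, the eligibility checklist is marked at screening only in every cohort, so it does not set Cohort 1 apart. Both points are correct. They also mean that the schedule is where the clamp-day test is specified for the other cohorts, and a blank there leaves nothing else to require it in Cohort 1.

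Existing controls reduce the risk. In the listed order, Cohort 1 women have two tests before the clamp, as many as women in Cohorts 2, 3 and 5; the difference is that theirs do not include the clamp day. The tracers are stable isotopes, the risk section describes no hazard specific to pregnancy, and the sequencing note does not say that C will precede B. The MR safety screen on the day of each MR study (Section V, item 11.6) might identify a known pregnancy, although the protocol does not say that it asks. These points make the added risk small. They do not make the earlier result current.

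Finally, nothing suggests that the test was left out on purpose. A clerical omission is the likelier explanation, which supports a simple correction.

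**Conclusion.** The concern holds. As the schedule reads, Cohort 1 women have 2 scheduled tests over 3 sessions, and the untested session is their only one with a clamp and tracer. It is the one exception among 4 clamp-day columns and among all 11 visit columns. These figures count table cells and do not measure risk. The documents give neither the interval between Sessions B and C nor the number of women of child-bearing potential in Cohort 1, so the chance of a missed pregnancy cannot be calculated. In the listed order it should be small; it would be larger if Session C came first or long after Session B.

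The conclusion assumes that the blank cell is blank in the source PDF. The point concerns participant safety and consistency of the schedule, and it does not bear on the statistical conclusions. It should be corrected.

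**What to change.** Check the Cohort 1 table in the source PDF. If the Session C cell is blank there, mark the urine pregnancy test in it.

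In either case, add one sentence to the Session C text in Section V, item 4: a woman of child-bearing potential must have a negative urine pregnancy test that day before insulin is started. This also gives the existing Cohort 2 mark a matching instruction, and it works whatever the order of sessions. Session D needs no change, because the Cohort 5 table already schedules the test.

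The cost is one table cell, one sentence and one further urine test per eligible Cohort 1 woman. Sample size, power and analysis are unchanged.
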